### **Statistical Analysis Design**

Out of the seven nights of sleep studied, the five with the longest night of sleep will be used for analysis. The values from those five nights will be averaged for each patient.

Descriptive statistics will be applied to the data, in order to determine reliability and consistency among different data collection methods, since similar variables are collected by different means. Correlation of data collected by different methods will be performed in order to cross examine and further validate results.

We will compare the accuracy of the response to the STOP-Bang question “Do you snore?” to audio data from the Sleep Cycle app. We will also compare the amount of snoring reported to the nasal obstruction score of the NOSE questionnaire. We will compare the distribution of the STOP-Bang questionnaire results (low/medium/high risk of Obstructive Sleep Apnea) to the distribution of results from the sensors. We will compare the agreement in recommendation for follow-up between the STOP-Bang Questionnaire and the sensors. Last, we will collect the percentage of people in the adult orthodontic clinic that should be referred for further evaluation for potential intervention.

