The Epworth Sleepiness Scale collects information regarding the subject's likelihood of falling asleep during the following activities: sitting and reading, watching television, sitting in public, sitting in a car, lying down to rest, sitting and talking to someone, sitting quietly after lunch without alcohol, and while sitting in a car stopped in traffic.

The participants are then instructed to wear the Belun Ring for seven nights and simultaneously use the Sleep Cycle app.

Data collected from the Belun Ring includes the Respiratory Event Index (REI) (derived from total sleep time, heart rate variability, and O2 saturation changes), Sleep Efficiency (time participant is asleep divided by total time in bed), stress level, mean spO2 (%), Sleep Score (bAHI, Belun Ring's version of AHI), REM sleep (percentage), minimum spO2 (%), mean pulse rate (bpm), percent of time below 90% oxygen saturation, and total sleep time (minutes).

The Sleep Cycle app will collect the subject's time asleep, stages "Awake, Sleep, and Deep Sleep," sleep regularity, time to bed, time woken up, time in bed, sleep efficiency, heart rate, and time snoring. It also will record audio while the subject is asleep. During the night, the subject's

smartphone will be placed on their nightstand. The subjects also have the option to add “sleep notes” to give additional information about their night of sleep, for example, if they were feeling sick or if they exercised right before bed.

The subjects will return to the Case Western Reserve Orthodontic Clinic for their next orthodontic adjustment appointment. The subjects will return the Belun Ring to the clinic and we will download the data. The Sleep Cycle Score Report from each night will be collected by either sharing via WhatsApp, an encrypted messaging service, or recording the data points manually into an Excel spreadsheet.

Subjects will then complete a Follow-Up Questionnaire. They will record the dates they used the devices during sleep. Subjects will also indicate whether they had a “normal” night of sleep, or if they were experiencing sickness, allergies, or any other sleep disruptions that may have affected the data collected. They will also indicate whether they have a bed partner.

Participants will be referred for further evaluation, if needed.

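### Ring and app are compared only on five-night means: the plan has no night-level analysis, so the date-matched nights it collects cannot show same-night agreement or night-to-night repeatability

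*Combined protocol and SAP*

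**What the plan says.** Under Experimental design, participants are to "wear the Belun Ring for seven nights and simultaneously use the Sleep Cycle app". Nightly records exist for both devices. For the app, "The Sleep Cycle Score Report from each night will be collected"; the background text says that the ring records data on each night. Participants also list their dates of use in the Follow-Up Questionnaire. Three quantities come from both devices: time asleep, sleep efficiency, and pulse or heart rate. The ring alone gives bAHI.

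The Statistical Analysis Design section then reduces the data: "Out of the seven nights of sleep studied, the five with the longest night of sleep will be used for analysis", followed by "The values from those five nights will be averaged for each patient". The purpose is given next: "Descriptive statistics will be applied to the data, in order to determine reliability and consistency among different data collection methods". The one between-method statistic named is correlation: "Correlation of data collected by different methods will be performed in order to cross examine and further validate results". The section mentions no repeated-measures model, within-person SD, ICC or limits of agreement. It does not say whether a device result is meant for one night or for a multi-night mean.

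**The concern.** Two devices recording the same person on the same night give the most direct evidence of whether they are consistent with each other. Up to 55 × 7 = 385 such pairs are collected, and the plan reduces them to 55 pairs of means. Once that is done, no within-person variance remains in the analysis data. Same-night agreement and each device's repeatability then cannot be estimated.

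What is at stake is interpretation. Averaging cancels part of the night-level disagreement, so differences between five-night means are tighter than differences on one night. Without a stated unit, a reader could take the averaged result as describing a single recording.

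**Working it through.** **Inputs.** From the documents: 55 participants, seven nights recorded, five analysed, one mean per participant. The documents give no SD, ICC, between-device correlation or AHI distribution, and no figure on this point to reproduce. All variance components below are assumptions. The five nights are treated as a random sample of nights, which sets aside the longest-night rule.

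**1. Sleep time in minutes.** Assume a between-person SD of 50, a true nightly SD of 60 and a nightly error SD of 30 per device. Let D be the SD of a fixed per-person ring-minus-app difference, split equally between the devices.

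- Correlation, one night: (50² + 60²) / (50² + 60² + 30² + D²/2) = 6100 / (7000 + D²/2)
- Correlation, five-night mean: (50² + 60²/5) / (50² + 60²/5 + 30²/5 + D²/2) = 3220 / (3400 + D²/2)
- Half-width of limits of agreement, one night: 1.96 √(2·30² + D²) = 1.96 √(1800 + D²)
- Half-width, five-night mean: 1.96 √(360 + D²)

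| D (min) | r, one night | r, mean | half-width, one night | half-width, mean |
|---|---|---|---|---|
| 0 | 0.87 | 0.95 | 83 | 37 |
| 30 | 0.82 | 0.84 | 102 | 70 |
| 35 | 0.80 | 0.80 | 108 | 78 |
| 45 | 0.76 | 0.73 | 121 | 96 |
| 60 | 0.69 | 0.62 | 144 | 123 |

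The limits narrow in every row. The correlation rises, stays level or falls. The crossover is where the devices rank people exactly as well as they track nights: 2500/(2500 + D²/2) = 3600/(3600 + 900) = 0.8, so D²/2 = 625 and D ≈ 35.

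At the other extreme, suppose the devices share only the person's level, with an independent nightly SD of 60 each. Averaging alone then takes r from 2500/6100 = 0.41 to 2500/3220 = 0.78.

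**2. The same in standardised form.** Let ICC be the between-person share of variance, rb the between-person device correlation and rw the same-night within-person device correlation, with k nights averaged.

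- One night: r = ICC·rb + (1 − ICC)·rw
- Mean of k: r = [ICC·rb + (1 − ICC)·rw/k] / [ICC + (1 − ICC)/k]
- Variance of the difference: 2·ICC·(1 − rb) + 2·(1 − ICC)·(1 − rw), the second term divided by k for a mean

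Over rb 0.6–0.9, ICC 0.3–0.9 and rw 0–0.9 with k = 5, the limits on the mean were 0.48 to 0.99 of the single-night width. With rb = 0.8 and ICC = 0.5, r goes from 0.40 to 0.67 at rw = 0, from 0.55 to 0.72 at rw = 0.3 (limits 0.62 of single-night width), and from 0.85 down to 0.82 at rw = 0.9.

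**3. Can 55 participants support a night-level ICC?** Simulation with the one-way ANOVA estimator (4,000 runs, seven nights) puts 95% of estimates in 0.37–0.61 for a true ICC of 0.5, and in 0.59–0.78 for a true ICC of 0.7. Restricting sleep time to the longest five of seven nights distorts this: a true 0.5 appears as about 0.65 and a true 0.7 as about 0.80. That is a reason to use all recorded nights.

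**4. Change of AHI band across seven nights (cut-offs 5, 15, 30).** Assume a lognormal AHI across people with log-SD 1 and median 4. At a nightly CV of 40–60%, about 53–62% of people change band at least once if nightly variation is centred on the person's mean, and 56–68% if it is lognormal around the person's median. At a CV of 20% the figure is about 32%. Over CV 20–60% it is 17–37% at median 2 and 40–74% at median 6. This illustrates what a mean hides about the ring. It says nothing about ring-app agreement, because the app does not report AHI.

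**The case against.** The best defence is that this is a descriptive cross-sectional study of a clinic population, and a multi-night mean is a legitimate summary of a person's usual sleep. The listed comparisons (reported snoring against app audio, snoring against the NOSE score, STOP-Bang risk against the sensors, agreement on follow-up, percentage referred) are all at the level of the person. That stands. Only the general ring-app comparison is affected, and the means should stay for the rest.

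Four stronger readings are tempting, and the documents do not support them.

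- **The plan breaks a promise of night-to-night reliability.** Its wording is "in order to determine reliability and consistency among different data collection methods, since similar variables are collected by different means". That is reliability between methods, and it can be examined on means. The night-level analysis is missing; it was not promised.
- **Averaging always makes the devices look better.** Correlation is the only between-method statistic named, and it can fall. The narrowing is general only for the spread of differences, and the plan does not propose limits of agreement.
- **The devices are used for one night, so the mean is the wrong target.** No document sets a single-night target. The ring is worn for seven nights, and the background describes app data being aggregated over time.
- **The information is lost.** It is absent only from the averaged data set. The nightly records and dates of use are collected.

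**Conclusion.** The point holds as a gap in the analysis. As written, any ring-app result describes five-night means and should not be read as same-night agreement, and neither device's repeatability can be reported. That limits of agreement are narrower on means requires only that same-night values within a person are not perfectly correlated. The amount rests entirely on assumed variance components. In the sleep-time illustration the half-width falls from 83 to 37 minutes with no per-person device difference, but only from 144 to 123 with a large one. The direction of any change in correlation is not determined. The band-change percentages depend strongly on the assumed median and CV and should not be quoted as expected results. The study can run without the change. This is a cheap improvement.

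**What to change.** Add a night-level analysis beside the averaged one.

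1. For time asleep, sleep efficiency and pulse or heart rate, pair ring and app by calendar night and use every recorded night.
2. Fit a mixed model to the ring-minus-app difference with a participant random intercept. Report the mean difference and repeated-measures limits of agreement, mean ± 1.96 √(between-participant variance + within-participant variance). Dividing the within-participant variance by k gives the limits for a k-night mean, so one model serves both targets.
3. Report a night-to-night ICC for each device, including bAHI for the ring. The share of participants whose bAHI band changes across nights can be added as a descriptive figure.
4. Keep participant means for comparisons with the questionnaires.
5. State for each device result whether it refers to one night or to a multi-night mean.

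The cost is some added SAP wording and a slightly longer analysis, with no new data. The single-night limits will look wider than those on the means, and the report should say why.

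### For sleep time, and efficiency if defined alike, ring and app record one quantity on the same nights, but the only specific validation statistic named is correlation, which cannot show agreement

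*Combined protocol and SAP*

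**What the plan says.** Under Experimental design, participants are "instructed to wear the Belun Ring for seven nights and simultaneously use the Sleep Cycle app". The two lists of recorded variables overlap:

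- **Sleep time.** The ring's list ends "mean pulse rate (bpm), percent of time below 90% oxygen saturation, and total sleep time (minutes"). The app collects time asleep.
- **Sleep efficiency.** For the ring this is defined: "Sleep Efficiency (time participant is asleep divided by total time in bed"). The app's list includes "time woken up, time in bed, sleep efficiency, heart rate, and time snoring", with no definition of efficiency.
- **Heart rate.** The ring gives a mean pulse rate and the app a heart rate. The participant's "smartphone will be placed on their nightstand", and the documents do not say how the app obtains the value.

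The Statistical Analysis Design notes that similar variables come from different sources. It assigns descriptive statistics, not further specified, to reliability and consistency, and adds: "Correlation of data collected by different methods will be performed in order to cross examine and further validate results". It names no paired difference, limits of agreement, intraclass or concordance coefficient, or acceptable difference for any continuous pair. The word agreement appears there once, for the categorical follow-up recommendation (STOP-Bang against the sensors).

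On nights, the same section says: "Out of the seven nights of sleep studied, the five with the longest night of sleep will be used for analysis". The values are then averaged per patient. The device whose sleep time does the ranking is not stated.

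**The concern.** When two devices measure the same quantity in the same units on the same night, the useful question is how far apart their readings are. Correlation answers a different one: whether people who rank high on one device also rank high on the other. A constant offset leaves r unchanged. A more varied sample raises r although the devices disagree by just as many minutes.

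The planned descriptive statistics may show a difference between the device means. Nothing named would show the spread of individual ring-minus-app differences. An r could then be reported as validation while a reader who wants to rely on either device's sleep time still does not know the likely error for one person.

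**Working it through.** **The plan's own figure.** The plan gives no agreement figure to reproduce. Its one sample-size figure, 55 participants at 80% power, cannot be reproduced because alpha, effect size and target parameter are not stated. At an assumed two-sided 0.05 it would fit a correlation of tanh((1.960 + 0.842)/√52) = 0.37, or equally a paired standardized difference of 2.802/√55 = 0.38. That is a separate matter; only n = 55 is used below.

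**Step 1: offset.** Assume a between-person SD of 50 min, an SD of differences of 25 min, and a constant app offset b.

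- r = 50/√(50² + 25²) = 0.894, whatever b is.
- Limits of agreement = b ± 1.96 × 25 = b ± 49 min. For b = 0, 30 and 60 they are −49 to +49, −19 to +79 and +11 to +109 min.

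**Step 2: what r and the limits look like for five-night means.** All SDs are assumptions, in minutes: between-person sb = 45, night-to-night sn = 60, nightly device error se = 45 or 60 per device, persistent person-specific device error sp = 0 or 30 per device.

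- Shared variance T = sb² + sn²/5 = 2025 + 720 = 2745.
- Error variance per device E = sp² + se²/5.
- r = T/(T + E); SD of difference = √(2E); limits = ±1.96 SD; with zero bias, median absolute difference = 0.6745 SD.

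| sp | se | E | r | SD of difference | Limits | Median |
|---|---|---|---|---|---|---|
| 0 | 45 | 405 | 0.871 | 28.5 | ±55.8 | 19.2 |
| 0 | 60 | 720 | 0.792 | 37.9 | ±74.4 | 25.6 |
| 30 | 45 | 1305 | 0.678 | 51.1 | ±100.1 | 34.5 |
| 30 | 60 | 1620 | 0.629 | 56.9 | ±111.6 | 38.4 |

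For single nights (divide by 1 instead of 5) the limits are ±124.7 and ±166.3 min with sp = 0, and ±149.9 and ±185.9 min with sp = 30.

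**Step 3: spread between people.** Keep sp = 0 and change only sb from 30 to 60, so T goes from 900 + 720 = 1620 to 3600 + 720 = 4320.

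- se = 45: r goes from 1620/2025 = 0.80 to 4320/4725 = 0.91; limits stay at ±55.8.
- se = 60: r goes from 1620/2340 = 0.69 to 4320/5040 = 0.86; limits stay at ±74.4.

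**Step 4: can 55 people support limits of agreement?** The 95% CI half-width of one five-night limit is t(54) × SD × √(1/55 + 1.96²/108) = 2.005 × 0.232 × SD ≈ 0.465 SD. That gives ±13.2 and ±17.6 min (sp = 0), or ±23.7 and ±26.5 min (sp = 30). The limits are estimable.

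**Step 5: the five-longest-nights rule.** Step 2 treats the five nights as unselected. A simulation of 200,000 people with seven nights each and the SDs of step 2 gave the following:

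- One device ranks the nights and both use those nights: the mean difference shifts about 11 min (se = 45) to 18 min (se = 60) toward the ranking device, because nights are chosen partly for that device's positive errors. With sp = 0 the limits are ±54.8 and ±72.6 min.
- Each device picks its own five nights: the shift is near zero, and the limits are about ±52 and ±69 min.
- Nights ranked by the mean of the two devices: no shift when the device errors are equal.

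**The case against.** The strongest case against is about scope. The study is descriptive, and its objective is to investigate sleep in a clinic population. The specific comparisons listed concern snoring, the NOSE score, STOP-Bang risk, follow-up recommendation and referral percentage. None compares the ring with the app on sleep time or efficiency. The correlation sentence is general, and the unspecified descriptive statistics neither promise nor exclude paired differences. All of this stands and lowers the weight of the point. It does not remove it: the plan says correlation will validate results across methods, and for a shared quantity it cannot.

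Two further objections also stand. The documents define sleep efficiency for the ring only, so it may not be a shared quantity; it is also bounded at 100%, so the spread of differences may change with level. And every magnitude above is assumed: adding the person-specific error alone takes the limits from ±56 to ±74 min up to ±100 to ±112 min, so the figures illustrate the argument and do not size a problem in this study.

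A reader might infer three stronger claims that the documents do not support:

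- **That the listed results are compromised.** No listed comparison uses a ring-versus-app correlation of sleep time or efficiency.
- **That the plan offers nothing but correlation on consistency.** The descriptive statistics are there, though unspecified.
- **That the two devices' five-night means come from different nights and so cannot be compared.** The natural reading is one set of five nights per patient. Even with separate selection, step 5 shows little harm when device errors are equal. Selection by one device is what distorts the bias.

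**Conclusion.** The point holds in a limited form. Correlation is the only specific statistic named for validating methods against each other. For sleep time, and for sleep efficiency if the two definitions match, it cannot show agreement. That conclusion is algebraic and does not depend on the assumed SDs; the minutes do, and also on independent device errors of equal size.

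What is affected is any statement that one method validates another. Neither device is a reference standard here, so even the better analysis would show agreement, not accuracy. This is a cheap improvement of lower severity.

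**What to change.** In the Statistical Analysis Design:

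1. For each quantity confirmed to be defined alike on both devices, make the main agreement analysis the paired ring-minus-app difference on all nights with both recordings. Use a model with a participant random effect, and report the bias and 95% limits of agreement, each with a 95% CI.
2. Check whether the spread of differences changes with level, especially for efficiency.
3. If five-night means are also compared, use the same nights for both devices and state how the nights are ranked. Do not read the bias as device offset when one device does the ranking. Take the bias from the all-night analysis, or rank nights by the mean of the two devices, bearing in mind that the absence of a shift in step 5 was seen with equal device errors.
4. Include heart rate only if the app gives a nightly value comparable with the ring's mean pulse rate.
5. Keep correlation as a secondary description, and for pairs that measure different constructs.
6. State that neither device is a reference standard.

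The cost is analysis wording and slightly more programming. No new data are needed: "The Sleep Cycle Score Report from each night will be collected", the ring data are downloaded, and the follow-up questionnaire records the dates of use, so nights can be paired. The figures will look less favourable than r, and the per-night limits will be wider than the five-night ones, which the report must explain.

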#### STOP-Bang Questionnaire

*Please answer the following questions by checking “yes” or “no” for each one*

	Yes	No
Snoring (Do you snore loudly?)		
Tiredness (Do you often feel tired, fatigued, or sleepy during the daytime?)		
Observed Apnea (Has anyone observed that you stop breathing, or choke or gasp during your sleep?)		
High Blood Pressure (Do you have or are you being treated for high blood pressure?)		
BMI (Is your body mass index more than 35 kg per m  ?)		
Age (Are you older than 50 years?)		
Neck Circumference (Is your neck circumference greater than 40 cm [15.75 inches]?)		
Gender (Are you male?)		

*Score 1 point for each positive response.*

*Scoring interpretation: 0 to 2 = low risk, 3 or 4 = intermediate risk, ≥ 5 = high risk.*

The NOSE Score Questionnaire involves a series of responses that yield a numerical score representative of the severity of nasal obstruction. The participant provides their responses to a variety of prompts using a ranking system from “Not a problem” (0 points) to “Severe problem” (4 points). The numerical responses are added, then the sum is multiplied by 5, to provide a result of “mild,” “moderate,” “severe,” or “extreme” nasal obstruction.

Over the past one month, how much of a problem were the following conditions for you?

	Not a problem	Very mild problem	Moderate problem	Fairly bad problem	Severe problem
Nasal congestion or stuffiness	0	1	2	3	4
Nasal blockage or obstruction	0	1	2	3	4
Trouble breathing through my nose	0	1	2	3	4
Trouble sleeping	0	1	2	3	4
Unable to get enough air through my nose during exercise or exertion	0	1	2	3	4

NOSE score (multiply your total score x5)

Nasal obstruction severity classification: mild (5-25) | moderate (30-50) | severe (55-75) | extreme (80-100)

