## **Experimental design**

The project will be a descriptive cross-sectional study.

A total of 55 adult participants will be recruited from the Case Western Reserve Orthodontics Clinic, based on the sample size calculation with a power of 80%. Inclusion criteria: current adult patients in the Case Western Reserve Orthodontics Clinic, ages 20-75, willingness to give informed consent

and participate in study, owner of a smartphone, and ability to return the Belun Ring and complete follow-up questionnaire. Exclusion criteria: age <20, currently or with history of taking blood pressure medication, currently undergoing transverse or anterior-posterior orthodontic correction, and currently pregnant or trying to become pregnant.

Participants will provide informed consent and will be instructed on the steps of the study. Demographic information will be collected, including a participant identifier, age of participant, and sex of participant. The use of the Belun Ring will be demonstrated, and they will be instructed on use of the Sleep Cycle app. They will complete the NOSE Score Questionnaire, STOP-Bang Questionnaire, Insomnia Severity Index, PROMIS Sleep Disturbance Questionnaire, and the Epworth Sleepiness Scale (ESS).

Data collected from the STOP-Bang Questionnaire includes positive/negative responses to: snoring, tired, observed, pressure, BMI >35, age over 50, neck size large, male gender, and the resulting OSA risk assessment of low, intermediate, or high.

Data collected from the NOSE Questionnaire includes positive or negative responses to: nasal congestion or stuffiness, nasal blockage or obstruction, trouble breathing through my nose, trouble sleeping, unable to get enough air through my nose during exercise or exertion, and the resulting classification of severity of nasal obstruction (mild, moderate, severe, extreme).

Data collected from the Insomnia Severity Index include difficulty falling or staying asleep, problem with waking up too early, satisfaction level with current sleep pattern, noticeability of subject's sleep problem to others, and amount of distress regarding current sleep habits.

Data collected from the PROMIS Sleep Disturbance Questionnaire includes level of agreement with statements about the subject's ability to fall asleep, quality of sleep, amount of sleep, level of satisfaction with their sleep, ability to stay asleep throughout the night.

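### The snoring comparison judges the accuracy of an any-snoring answer, but the form asks about loud snoring and no loudness scoring of the app data is described

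*Combined protocol and SAP*

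**What the plan says.** All references are to the combined protocol and SAP.

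- **Statistical Analysis Design:** "We will compare the accuracy of the response to the STOP-Bang question “Do you snore?” to audio data from the Sleep Cycle app". The item is cited without any reference to loudness.
- **STOP-Bang Questionnaire (the form):** the item participants tick Yes or No begins "Snoring (Do you snore loudly".
- **Experimental design, STOP-Bang data:** the answers are stored as "positive/negative responses to: snoring, tired, observed, pressure" and so on, so the loudness qualifier is absent here too.
- **Experimental design, app data:** the listed outputs end with "time in bed, sleep efficiency, heart rate, and time snoring". The section adds: "It also will record audio while the subject is asleep". The "smartphone will be placed on their nightstand", with no distance or calibration given.
- **Experimental design, data collection:** at the return visit the nightly score report is shared or its values are entered by hand. Retrieval of the audio files is not described.
- **Background text on smartphone apps, before Objectives:** the app deletes stored audio automatically after 20 nights.

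**The concern.** The self-report item and its reference may measure different things. The item asks about loudness; the one listed app metric measures how long snoring lasts. Someone who snores quietly and answers No has answered correctly, yet an analysis that treats the item as a question about any snoring can count that answer as an error.

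At stake is one stated result. The study could report that orthodontic patients misjudge their own snoring when the two sources simply answered different questions. The STOP-Bang total and its risk classes do not depend on this comparison.

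**Working it through.** **Plan's own figure.** The plan gives none for this comparison. The recruitment target of 55 serves below only as a denominator.

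**Step 1: the texts side by side.**

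| Element | What the documents give | Construct |
|---|---|---|
| Item administered | Yes/No to loud snoring | Loudness |
| Item as cited in the analysis | Yes/No to snoring | Any snoring |
| App metric listed | Time snoring | Duration |
| App audio | Recorded; no scoring step, threshold or retrieval described | Undefined |

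No row supplies a loudness reference for the item administered. Nor can a later review of the audio be assumed: recordings are deleted after 20 nights, and the return visit is the next orthodontic appointment, whose timing is not given.

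**Step 2: consequence if any app-detected snoring counts as positive.** Assume that everyone answers truthfully and the app detects all snoring. Let *a* be the share who snore at all and *l* the share who snore loudly. Every Yes is then scored right, and the No answers scored wrong come from the quiet snorers:

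- No answers scored wrong = 55 × (*a* − *l*)
- Apparent accuracy = 1 − (*a* − *l*)

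The documents give neither share. With assumed values of 40 to 60% for *a* and 20 to 25% for *l*:

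- Low end: 55 × (0.40 − 0.25) = 8.3 scored wrong; apparent accuracy 1 − 0.15 = 85%.
- High end: 55 × (0.60 − 0.20) = 22.0 scored wrong; apparent accuracy 1 − 0.40 = 60%.

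True accuracy for the question asked is 100% throughout. A wider assumption, with 40 to 70% snoring and 30 to 70% of those loud, gives 55 × 0.40 × 0.30 = 6.6 to 55 × 0.70 × 0.70 = 27.0. The mechanism is certain under this rule; the count depends wholly on the assumed shares.

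**Step 3: precision of a comparison that needs no cut.** With 20 to 25% answering Yes, there are 55 × 0.20 = 11 to 55 × 0.25 = 13.75, about 14, Yes responders. The 95% half-width for the difference in mean time snoring, in SD units, is t(0.975, 53) × √(1/n₁ + 1/n₂), with t = 2.006:

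- 11 versus 44: 2.006 × √(0.0909 + 0.0227) = 0.68 SD.
- 14 versus 41: 2.006 × √(0.0714 + 0.0244) = 0.62 SD.

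This assumes 55 complete participants and equal variances.

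**The case against.** **The wording may be shorthand.** The Experimental design section abbreviates all STOP-Bang items, and the analysis section writes medium where the form says intermediate. The printed form fixes what is asked. This stands as far as it goes: nothing shows that the investigators would read No as a denial of any snoring. But even if the wording is only corrected editorially, the reference remains a duration or unscored audio.

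**Loudness could be judged from the audio.** The plan names audio data, and listening to the recordings is not excluded. That is fair, and it is why the conclusion is that a truthful No can be scored wrong, not that it will be. No such step is described, however, and retrieval of the audio is not provided for.

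**Stronger readings that the documents do not support.**

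- A reader might infer that the plan formally tests accuracy. It describes a comparison within a descriptive study and names no test.
- A reader might infer a direction of bias, such as under-reporting under an any-snoring rule and over-reporting under a strict duration cut. The second depends entirely on chosen inputs. If a cut misses 30 to 50% of loud snorers, 55 × 0.20 × 0.30 = 3.3 to 55 × 0.25 × 0.50 = 6.9 Yes answers are scored wrong. If it catches up to 10% of quiet snorers, at most 55 × 0.40 × 0.10 = 2.2 No answers are. Raise that catch to 20% and the maximum is 4.4, above the lowest Yes count, so the ordering no longer holds.
- A reader might infer that a bed partner's snoring contaminates the app data. Partner status is collected ("They will also indicate whether they have a bed partner") and enters no stated analysis, but the documents do not say whether the app separates sleepers. The follow-up questionnaire asks about "any other sleep disruptions that may have affected the data collected" and sleep notes are optional, so there is some route to flag affected nights. This is a separate, unquantified matter.

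**Conclusion.** The concern holds as a minor point. The analysis section cites a different question from the one administered, and no described app measure captures loudness. Following the plan as written can therefore label a quiet snorer's truthful No as inaccurate.

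Under an any-snoring rule the loss equals the share who snore but not loudly: 8 to 22 of 55 under the assumed 40 to 60% and 20 to 25%, truthful answers and perfect detection. That range illustrates the mechanism and does not estimate its size in this clinic. Under any other rule, size and direction are undetermined. Confidence is high in the textual mismatch and in the absence of a described loudness rule; it does not extend to the magnitude.

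**What to change.** In the Statistical Analysis Design section:

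1. Quote the snoring item as administered, and state that No is not read as a denial of any snoring.
2. Replace accuracy with agreement between self-reported loud snoring and app-detected snoring, and state that app time snoring measures duration, not loudness.
3. Compare time snoring, averaged over the five analysed nights as already planned, between Yes and No responders as a continuous measure. This fits the correlation between methods that the plan already includes.
4. If a cut for app-positive snoring is used, fix it before looking at the data.

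This does not turn duration into loudness; it stops the disagreement from being reported as faulty self-report. It also makes time snoring the explicit comparator in place of unspecified audio data, and the revised text should say so.

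**Cost.** A wording change and one added comparison, with no new data. The drawback is low precision: with a half-width of about 0.62 to 0.68 SD, only a sizeable Yes–No difference would be clear.

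**Optional and secondary.** Tabulate the app-snoring comparison by the bed-partner status already collected. This is descriptive only: it would not remove any contamination, and the strata would be small.
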